**Protocol Approval**

## Synopsis

Title	Peanut Sublingual Immunotherapy and Induction of Clinical Tolerance in Peanut Allergic Children (TLC)
Short Title	Peanut SLIT and Tolerance
Clinical Phase	Phase I/II – Safety and Efficacy
IND	14326
Sponsor	A. [name]
Principal Investigator	A. [name]
Participating Site	University of North Carolina at Chapel Hill (after March 26, 2012) Prior to March 26, 2012: Duke University Medical Center, Durham, NC
Accrual Objective	55 subjects to allow for 45 subjects to complete study interventions
Study Design	A prospective, randomized open-label study to assess the induction of desensitization after at least 48 months of peanut sublingual immunotherapy (SLIT) and the persistence of desensitization (sustained unresponsiveness) following a period of up to 17 weeks of peanut avoidance.
Study Duration	Up to 66 months per subject; Duration varies dependent upon subject’s randomized period of study drug withholding.
Primary Endpoints	
 
• An estimate of the population sensitization threshold as assessed by the 48th month DBPCFC, predicted to provoke reactions in 5% and 10% of the peanut-allergic population.
 
• Multiplicative or differential change in the population sensitization threshold as assessed by the 48th month DBPCFC with a unit change in covariates.
 
• An estimate of time to loss of desensitization for the following events:             
 
- Subject's true sensitivity threshold to reduce by half.
 
- Subject's true sensitivity threshold to maintain at the same level of LOAEL.
 
- Subject's true sensitivity threshold to drop by at least one level of LOAEL.
 
- Subject's true sensitivity threshold to remain at or above MCRT.
 
 
 
• Estimates of the proportion of patients at a fixed time for any of the above events that define loss of desensitization.
 
• Multiplicative change in hazard of loss of desensitization with a unit change in covariates.
 

Secondary Endpoints	
 
• Comparative estimates of changes in immune parameters over time among subjects who were induced with clinical desensitization versus those who failed. Changes coinciding with the loss of desensitization would also be studied.
 
• Incidence of all adverse events and serious adverse events during the study.
 
• Incidence of all gastrointestinal and possible gastrointestinal eosinophilic adverse events.
 

Inclusion Criteria	
 
• Age 1-11 years of either sex, any race, any ethnicity with a convincing clinical history of peanut allergy or an in vitro peanut-specific IgE [CAP-FEIA] > 0.35 kUA/L; and,
 
• A positive result to 1000 mg peanut protein DBPCFC after enrollment (during screening or baseline visit); and,
 
• Written consent including assent where indicated
 
 
OR
 
 
• Duke IRB approved enrollment exception for those subjects from Duke IRB Pro0003579, UNC IRB 11-2301, “Sublingual Immunotherapy for Peanut Allergy: A Randomized, Double-Blind, Placebo-Controlled, Phase I/II Pilot Study with a Whole Peanut Extract, CoFAR 4” who did not pass the 164 week (3 years) end of study 10 gm peanut DBPCFC.
 


Exclusion Criteria
	
 
• History of severe anaphylaxis to peanut, defined as hypoxia, hypotension, or neurologic compromise (cyanosis or SpO2 < 92% at any stage, hypotension, confusion, collapse, loss of consciousness, or incontinence)
 
• Participation in any interventional study for the treatment of food allergy in the past 6 months, unless an exception is IRB approved
 
• Known oat, wheat, or glycerin allergy
 
• Eosinophilic or other inflammatory (e.g. celiac) gastrointestinal disease
 
• Severe asthma (2007 NHLBI Criteria Steps 5 or 6 – Appendix 2)
 
• Inability to discontinue antihistamines for skin testing and DBPCFCs
 
• Use of omalizumab or other non-traditional forms of allergen immunotherapy (e.g., oral or sublingual) or immunomodulator therapy (not including corticosteroids) or biologic therapy within the past year
 
• Use of <math>\beta</math>-blockers (oral), angiotensin-converting enzyme (ACE) inhibitors, angiotensin-receptor blockers (ARB) or calcium channel blockers
 
• Significant medical condition (e.g., liver, kidney, gastrointestinal, cardiovascular, hematologic, or pulmonary disease) which would put the subject at risk for induction of food reactions
 
																																																																																										

Study Intervention Description
	
The study is a prospective, randomized, open-label trial based on previous experience at Duke University with peanut-allergic subjects. We will enroll 55 participants to receive at least 48 months of open label peanut SLIT and continue with study interventions described.
 
The peanut SLIT study drug Build-Up Phase dosing (approximately 20 weeks) is outlined below.
 
  
 Dose #	Peanut Dilution	Pumps	Dose of Peanut Protein	Interval in Weeks	% Increase	
   
1	1/100	1	2.5 mcg		-	
 
2	1/100	2	5 mcg	1	100%	
 
3	1/100	4	10 mcg	1	100%	
 
4	1/100	8	20 mcg	1	100%	
 
5	1/10	1	25 mcg	1	25%	
 
6	1/10	2	50 mcg	1	100%	
 
7	1/10	4	100 mcg	1	100%	
 
8	1/10	8	200 mcg	1	100%	
 
9	Full concentration	1	250 mcg	2	25%	
 
10	Full concentration	2	500 mcg	2	100%	
 
11	Full concentration	4	1000 mcg	2	100%	
 
12	Full concentration	8	2000 mcg	2	100%	
 
13	Full concentration	12	3000 mcg	2	50%	
 
14	Full concentration	16	4000 mcg	2	33%	
  
 
After completing the build-up phase, subjects will continue on a daily maintenance dose of 4000 mcg of peanut protein via SLIT doses.
 
Following at least 48 months of open SLIT study drug (including the build-up phase), subjects will undergo a DBPCFC to verify desensitization (i.e., an increase in reaction threshold while receiving peanut SLIT study drug).
	Dose #	Peanut Dilution	Pumps	Dose of Peanut Protein	Interval in Weeks	% Increase	1	1/100	1	2.5 mcg		-	2	1/100	2	5 mcg	1	100%	3	1/100	4	10 mcg	1	100%	4	1/100	8	20 mcg	1	100%	5	1/10	1	25 mcg	1	25%	6	1/10	2	50 mcg	1	100%	7	1/10	4	100 mcg	1	100%	8	1/10	8	200 mcg	1	100%	9	Full concentration	1	250 mcg	2	25%	10	Full concentration	2	500 mcg	2	100%	11	Full concentration	4	1000 mcg	2	100%	12	Full concentration	8	2000 mcg	2	100%	13	Full concentration	12	3000 mcg	2	50%	14	Full concentration	16	4000 mcg	2	33%
Dose #	Peanut Dilution	Pumps	Dose of Peanut Protein	Interval in Weeks	% Increase																																																																																						
1	1/100	1	2.5 mcg		-																																																																																						
2	1/100	2	5 mcg	1	100%																																																																																						
3	1/100	4	10 mcg	1	100%																																																																																						
4	1/100	8	20 mcg	1	100%																																																																																						
5	1/10	1	25 mcg	1	25%																																																																																						
6	1/10	2	50 mcg	1	100%																																																																																						
7	1/10	4	100 mcg	1	100%																																																																																						
8	1/10	8	200 mcg	1	100%																																																																																						
9	Full concentration	1	250 mcg	2	25%																																																																																						
10	Full concentration	2	500 mcg	2	100%																																																																																						
11	Full concentration	4	1000 mcg	2	100%																																																																																						
12	Full concentration	8	2000 mcg	2	100%																																																																																						
13	Full concentration	12	3000 mcg	2	50%																																																																																						
14	Full concentration	16	4000 mcg	2	33%																																																																																						

	
 
• Subjects who are unable to consume > (more than) 300 mg of peanut protein without symptoms will complete the study and not proceed to further evaluations. These subjects will be recommended to resume strict peanut avoidance.
 
• Subjects who are able to consume <math>\geq</math> (greater than or equal to) 300 mg of peanut protein without symptoms will be randomized to withhold study drug and all peanut consumption for a period between 1 and 17 weeks. This avoidance period will be followed by a DBPCFC to assess persistence of the desensitization effect (sustained unresponsiveness).        After this final DBPCFC, the study will be completed and the subject will be recommended to transition to a daily peanut food equivalent.
 

Study Procedures
	
The following procedures will be performed according to the schedule in Appendix 1:
 
 
• Medical and allergy history (including dietary history)
 
• Physical examination
 
• Peak flow rates (if capable)
 
• Serum analysis for peanut-specific immunoglobulins (ImmunoCAP)
 
• Whole blood for basophil activation and T-cell studies
 
• Sublingual Immunotherapy (SLIT)
 
• Double-blind, placebo-controlled, food challenge (DBPCFC) to peanut
 
• Endpoint titration peanut skin prick testing
 
• Saliva collection for immunoglobulin studies
 

Study Stopping Rules
	
 
• Any death related to study drug dosing.
 
• Greater than 2 severe anaphylactic reactions related to study drug dosing at any stage of the protocol.
 
• Greater than 3 subjects who require more than 1 intramuscular epinephrine injection during dose escalation or maintenance dosing of study drug.
 
 
If any of the above occurs, enrollment and uposing will be halted until there's a review by the DSMB, FDA, and IRB.

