## STUDY DESIGN

This SLIT study is a prospective, randomized, open-label study based on previous experience at Duke University Medical Center using OIT and SLIT in food allergic subjects. The study will enroll 55 participants with peanut allergy with a goal of 50 children completing protocol interventions. Upon enrollment, all subjects will undergo an entry DBPCFC with 1000 mg of peanut protein to confirm the peanut allergy diagnosis and establish a baseline threshold level. Following a positive DBPCFC, each subject will begin the study drug with peanut SLIT at a starting dose of 1 pump of a 1/100 dilution of peanut concentrate (2500 mcg peanut protein). During the build-up phase which lasts approximately 20 weeks (Table 1), subjects will dose daily and increase the number of pumps every 1-2 weeks as per the dosing schedule. Subjects return to the research unit for observed dosing with each change in peanut SLIT dilution (1/100, 1/10, full concentration) and with every other dose increase on full concentration until the maintenance dose of 16 pumps of full concentration peanut SLIT (4000 mcg peanut protein) is achieved. Subjects will then continue daily administration of the maintenance dose and return every 6 months for follow-up.

After at least 48 months of peanut SLIT study drug, subjects will undergo a second DBPCFC to 5000 mg of peanut protein to assess desensitization.

- Subjects who are not desensitized are those who are not able to consume more than the MCRT without symptoms, which has been defined as 300 mg of peanut protein. Subjects who consume less than 300 mg of peanut protein without symptoms will stop peanut SLIT and conclude the study. These subjects will not undergo any additional study procedures including the remaining protocol DBPCFCs and will be recommended to resume a strict peanut avoidance diet.
- Subjects who are able to consume more than 300 mg of peanut protein will be randomized to an interval between 1 and 17 weeks during which all peanut including peanut SLIT study drug will be discontinued. This period of avoidance will be followed by a third DBPCFC to 5000 mg of peanut protein to evaluate for the loss of the desensitization effect. After this final DBPCFC, the study will be completed for these subjects. At the primary investigators clinical discretion, they will be recommended to transition to a daily peanut food equivalent to maintain the desensitized effect.

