## 2.2 Study Endpoints

### 2.2.1 Primary Endpoint

The primary efficacy endpoints are:

- An estimate of the dose as assessed by the 48th month DBPCFC, also called population sensitization threshold, predicted to provoke reactions in 5% and 10% of the peanut-allergic population. This will also give population level NOAEL and LOAEL that would define interval of consecutive administered dose levels within which the population sensitization threshold lies.
- Multiplicative or differential change in the population sensitization threshold as assessed by the 48th month DBPCFC with a unit change in covariates.
- An estimate of time to loss of desensitization for the following events:

- Subject's true sensitivity threshold to reduce by half, also called half-life of sensitivity threshold.
- Subject's true sensitivity threshold to maintain at the same level of LOAEL.
- Subject's true sensitivity threshold to drop by at least one level of LOAEL.
- Subject's true sensitivity threshold to remain at or above MCRT.
- Estimates of the proportion of patients at a fixed time for any of the above events that define loss of desensitization (bullet 2).
- Multiplicative change in hazard of loss of desensitization with a unit change in covariates.

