### **5.2 Enrollment**

Up to 55 children may be enrolled in this protocol, including the participant allowed under an exception to enroll from the CoFAR 4 Pro0003579 (not counted in the data analysis for this study). Accounting for a 10% drop out rate, we anticipate having approximately 45 children eligible for randomization during the blinded phase of the study.

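### The month-48 decision rule gives opposite instructions for a child who tolerates exactly 300 mg, and the SAP leaves the underlying dose scale unstated

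*Protocol*

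**What the plan says.** The Synopsis (Study Intervention Description) gives two rules. Children unable to consume an amount "more than) 300 mg of peanut protein without symptoms will complete the study and not proceed to further evaluations". Children able to consume an amount "greater than or equal to) 300 mg of peanut protein without symptoms will be randomized to withhold study drug and all peanut consumption".

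The protocol's STUDY DESIGN section gives three statements: "Subjects who are not desensitized are those who are not able to consume more than the MCRT without symptoms"; "Subjects who consume less than 300 mg of peanut protein without symptoms will stop peanut SLIT and conclude the study"; and "Subjects who are able to consume more than 300 mg of peanut protein will be randomized to an interval between 1 and 17 weeks". Protocol 5.5 defines desensitization as a reaction threshold above 300 mg and randomizes every desensitized child.

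In the SAP:
- Section 4 repeats the definition as a reaction threshold above the MCRT and withholds the final challenge from children who fail.
- Section 4.3 item 1 admits a child who has no symptoms at a 300 mg dose. Item 2 records loss at week 0 for intolerable symptoms at or below the MCRT.
- Sections 8.1.1 and 8.1.2 tie the waived final challenge and the time-0 score to a LOAEL below the MCRT.
- Section 10.1 lists the NOAEL d as 100, 200, 500, 800, 1300 and 2100 mg, and sets the time to loss X_d to 0 when d is below the MCRT.

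One of the time-to-loss endpoints in Protocol 2.2.1 is the "true sensitivity threshold to remain at or above MCRT".

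**The concern.** A threshold rule should send every attainable result to one action. Here the challenge steps land exactly on the threshold, and the wording at that value is inconsistent within the Synopsis, within STUDY DESIGN, and between the two. The comparators in the Synopsis are spelled out in words, so this is not a symbol lost in text extraction.

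Both routes stop SLIT. The rule still decides:
- whether the child has a 1 to 17 week avoidance period and a third challenge;
- whether the child is in the ITT set, which SAP 7 defines as randomized patients;
- what peanut advice follows. A stopped child is told to avoid peanut strictly. A randomized child is recommended a food equivalent in the Synopsis; in STUDY DESIGN this is subject to the investigator ("clinical discretion, they will be recommended to transition to a daily peanut food equivalent"), and in Protocol 5.5 it is an option;
- whether the child enters the SAP 10.1 likelihood as a time-0 loss or through the distribution F_d.

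The unstated dose scale in the SAP affects the last of these directly.

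**Working it through.** **Inputs.** Challenge steps of 100, 200, 500, 800, 1300 and 2100 mg, with a stated total of 5000 mg (Protocol 5.6, SAP 4.2). MCRT = 300 mg (Protocol 2.1, SAP 4).

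**Step 1: reproduce the stated total.** The running sums are 100, 300, 800, 1600, 2900 and 5000 mg. The last matches the plan. The second equals the MCRT, and no single step is 300 mg.

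**Step 2: apply each rule to all seven outcomes.** Doses are single / cumulative, in mg. The protocol rules and SAP 4.3 item 1 are applied to the cumulative tolerated dose.

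| Steps tolerated | NOAEL | LOAEL | Synopsis | STUDY DESIGN orders | SAP 4.3 item 1 | SAP 10.1, d single | SAP 10.1, d cumulative | SAP 8.1.2, LOAEL single / cumulative |
|---|---|---|---|---|---|---|---|---|
| 0 | 0 / 0 | 100 / 100 | stop | stop | not admitted | X_d = 0 | X_d = 0 | 0 / 0 |
| 1 | 100 / 100 | 200 / 300 | stop | stop | not admitted | X_d = 0 | X_d = 0 | 0 / not 0 |
| 2 | 200 / 300 | 500 / 800 | stop and randomize | neither | randomize | X_d = 0 | F_d | not 0 / not 0 |
| 3 | 500 / 800 | 800 / 1600 | randomize | randomize | randomize | F_d | F_d | not 0 / not 0 |
| 4 | 800 / 1600 | 1300 / 2900 | randomize | randomize | randomize | F_d | F_d | not 0 / not 0 |
| 5 | 1300 / 2900 | 2100 / 5000 | randomize | randomize | randomize | F_d | F_d | not 0 / not 0 |
| 6 | 2100 / 5000 | none | randomize | randomize | randomize | F_d | F_d | not 0 / not 0 |

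The Synopsis, STUDY DESIGN and SAP 4.3 agree on six of the seven outcomes and conflict on one.

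**Step 3: the child at 300 mg, protocol.** Synopsis: 300 > 300 is false, so the study ends; 300 >= 300 is true, so the child is randomized. STUDY DESIGN: 300 < 300 and 300 > 300 are both false, so neither order applies, although the same section calls the child not desensitized.

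**Step 4: the same child, SAP.**
- Both cumulative: SAP 4.3 admits the child, and d = 300 is not below 300, so the child enters F_d. The sections agree.
- Both single: a tolerated dose of 200 does not reach 300, so the child is not admitted and X_d = 0. The sections agree.
- SAP 4.3 cumulative and SAP 10.1 as listed: the child is randomized, yet d = 200 < 300 gives X_d = 0. The sections disagree. SAP 8.1.2 also disagrees with that score, because the LOAEL (500 or 800) is not below 300.

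**Step 5: what reaction threshold means.** Read as the NOAEL, the child's value is 200 or 300, not above 300, so the child is not desensitized. Read as the eliciting dose, it is 500 or 800, so the child is desensitized and Protocol 5.5 randomizes.

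The rule for claiming sustained unresponsiveness (SU) in SAP 4 is also sensitive. For a child whose result is unchanged at the final challenge:
- NOAEL, single: 200 >= max(300, 200) is false.
- NOAEL, cumulative: 300 >= max(300, 300) is true.
- Eliciting dose: 500 >= max(300, 500) and 800 >= max(300, 800) are both true.

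**Step 6: size, illustration only.** The documents do not give the number k of children at exactly 300 mg. In an intercept-only version of the logistic part of SAP 10.1, moving k of n children between time-0 loss and F_d shifts the estimate of P(X = 0) by k/n.

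| Assumed k | n = 45 | n = 51 |
|---|---|---|
| 0 | 0 | 0 |
| 1 | 2.2 points | 2.0 points |
| 3 | 6.7 points | 5.9 points |
| 5 | 11.1 points | 9.8 points |

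The 45 comes from Protocol 5.2 ("we anticipate having approximately 45 children eligible for randomization") and the 51 is enrolment (Protocol 8.1.1). Neither is exactly the denominator of that likelihood.

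**The case against.** The strongest reply concerns the SAP. A reader might infer that the SAP plainly contradicts itself and scores this child as lost at time 0. The documents do not support that without a condition. It requires SAP 4.3 to be read cumulatively and SAP 10.1 as single doses, and Step 4 shows agreement on either common scale. SAP 4.3 item 2, read cumulatively, does not record a loss, because the reaction comes above the MCRT. Nor do SAP 8.1.1 and 8.1.2, on either scale. What stands is narrower. The scale is unstated, the wording of SAP 4.3 fits only the cumulative total, and the list in SAP 10.1 is of single doses.

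A reader might also infer that SAP 4 denies this child the final challenge, or that an unchanged child fails the SU rule. Both need reaction threshold to mean the NOAEL. SAP 8.1.1 makes that approximation for the true sensitivity threshold within the time-to-loss framework, not for the reaction threshold in SAP 4. On the eliciting-dose reading neither inference follows.

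A child who reacts at step 2 might look like a second conflict. SAP 4.3 item 2 covers that child on both scales when symptoms are intolerable, since 200 mg is below the MCRT and 300 mg is at it. Only the LOAEL wording of SAP 8.1.1 and 8.1.2 remains loose.

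Finally, choosing 300 mg or more over more than 300 mg decides who undergoes avoidance and another challenge, and Protocol 2.1, STUDY DESIGN and Protocol 5.5 use language of exceeding 300 mg. That is fair: the choice is the sponsor's. None of these replies removes the overlap in the Synopsis or the missing instruction in STUDY DESIGN.

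**Conclusion.** The rule is wrong as written at one of the seven attainable outcomes. At a cumulative 300 mg the Synopsis orders two opposite actions and STUDY DESIGN orders none. This rests only on the stated challenge steps and on applying the 300 mg threshold to the cumulative amount consumed.

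The SAP defect is an unstated dose scale. It becomes a contradiction between SAP 4.3 and SAP 10.1 only when the two sections are read on different scales.

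The practical effect cannot be sized from the documents, because the number of children affected is unknown and may be zero. The k/n figures show sensitivity under assumed counts and do not estimate bias. No effect on ED05, ED10 or the hazard estimates has been shown. The point should be corrected, but it does not undermine the design.

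**What to change.** Use one rule on the cumulative asymptomatic dose: below 300 mg ends the study, and 300 mg or more is randomized. This matches the second Synopsis rule, SAP 4.3 item 1 and the endpoint of staying at or above the MCRT. It also fits Protocol 5.5 and SAP 4 if reaction threshold is the eliciting dose: a reaction at step 2 (200 or 300 mg) is not above 300, and a reaction at step 3 (500 or 800 mg) is. If the sponsor prefers more than 300 mg, it should apply that rule throughout instead.

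- Align the Synopsis, STUDY DESIGN, Protocol 5.5, SAP 4 and SAP 4.3 items 1 and 2 to the chosen rule.
- State the cumulative scale once in SAP 3.2.3, where NOAEL and LOAEL are defined. Carry it through the dose cap in SAP 4.3 item 3, SAP 8.1.1 and 8.1.2, and the ED05 and ED10 analysis in SAP 10.1.
- In SAP 8.1.1 and 8.1.2, replace the LOAEL condition with a cumulative NOAEL below 300 mg.
- In the SAP 10.1 likelihood, list d as 100, 300, 800, 1600, 2900 and 5000 mg, with X_d = 0 only when d is below 300.
- Define reaction threshold in Protocol 5.5 and SAP 4, including for the SU rule.

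The cost is amended text plus one explicit decision by the sponsor at the boundary, with no new visits, data or patients. It should be settled before the remaining month-48 challenges are run; SAP 1 reports 24 children waiting for theirs.

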## Glossary of Abbreviations

AE	Adverse Event
CFR	Code of Federal Regulations
CRF	Case Report Form
CTC	Common Toxicity Criteria
CTRC	Clinical Translational Research Center
DBPCFCs = OFC	Double-Blind, Placebo-Controlled Food Challenges = Oral Food Challenge
DSMB	Data Safety Monitoring Board
EC	Ethics Committee
Enrolled	Signed consent
EPIT	Epicutaneous Immunotherapy
FDA	Food and Drug Administration
GCP	Good Clinical Practice
ICH	International Conference on Harmonization
IDS	Investigational Drug Service
IND	Investigational New Drug Application
IRB	Institutional Review Board
kU/L	Kilounits per Liter
MCRT	Minimal Clinically Relevant Threshold
NIAID	National Institute of Allergy and Infectious Diseases
OIT	Oral Immunotherapy
PBMC	Peripheral Blood Mononuclear Cells
PI	Principal Investigator
PST	Skin Prick Tests
SAE	Serious Adverse Event
SLIT	Sublingual Immunotherapy
SU	Sustained Unresponsiveness
TReg	T regulatory cell
UNC	University of North Carolina at Chapel Hill

